**Table 2. Summary of Key Study Design Features to Ensure Internal and External Validity**

Eligibility Criteria	Randomization	Treatment Fidelity	Missing Data
>90% pedometer accuracy	Unpredictable Blocks	Track with daily exercise logs and enhance with every 3 month follow-ups	Most common cause of missing data (health reasons) will be same for both arms
Able to collect $\geq 5$ of 10 days of valid baseline step count data	Allocation Concealment	Lack of treatment fidelity defined a priori as <70% days with exercise	Impute with least favorable value or carry forward previous values
	Blinding of RAs performing assessments	Sensitivity analysis accounting for treatment fidelity	Sensitivity analysis excluding subjects with missing data

The most important factor affecting compliance is the complexity of the intervention. Our experience indicates that the WEB program and pedometer intervention pose minimal participant burden. The WEB intervention is designed to foster compliance, using a dynamic website and immediate feedback. Subjects upload step counts and visit the website at their convenience. ESC, a similar study, has shown persistent engagement by participants at month 3, and similar retention and engagement has been shown at month 12 in a separate study. Our preliminary

data show that the use of graphs, messages, and tips by participants increases by month 3. In the current proposal, the intervention lasts 12 months, including a 6-month intensive intervention phase where the subject will have access to an interactive website with new content being posted about maintaining a walking program, as well as an online forum community, and step count goals. Following the intensive intervention phase, the 6-month maintenance phase will consist of access to the website to obtain new step count goal, as well as to upload pedometer data but no new educational content posted about a walking program. During the maintenance intervention phase (months 7-12), subjects will be able to access content posted previously about the walking program. We believe that maintaining a dynamic website with relevant and changing content will keep participants engaged in the intervention. Feedback from the graphs is most commonly used by participants and will encourage engagement. We will provide a user-friendly written guide to all the features of the website. We will measure treatment fidelity specific to the intervention group by tracking numbers of (1) no-wear days of the pedometer, (2) subjects who require telephone call reminders to upload, and (3) logins to the website.

### **Minimizing Attrition and Handling Missing Data**

We will do everything we can to minimize attrition and missing data. Our run-in period prior to randomization (when at least 10 days of baseline step counts are required to be collected from an eligible participant) will screen out those who may be potential drop-outs. Time spent with the healthcare provider, the continuity of care, and the communication style of providers may improve retention. We will structure the clinic visits and follow-up telephone contacts such that each participant interacts with the same research assistant on each occasion. Monetary compensation has been shown to be the best strategy to achieve protocol adherence and minimize missing outcomes data (78). We will disperse \$50 in payment to subjects at the baseline in-clinic study visit and a \$25 payment at each of the following in-clinic study visits (3-month, 6-month and 12-month) for their travel-related costs, time and effort. Additionally, subjects will be given the Fitbit Zip which was used during their participation at the end of the research study (up to 13 months). For both arms, the face-to-face clinic visits, the regularly scheduled telephone contacts between study staff and subjects, and the subject remuneration will aid in achieving our anticipated retention rate of at least 60% at 6 months. In our other COPD studies, our loss to follow-up is low, ranging from 0% to 4%, at 12 months.

Based on our previous work, medical problems and temporary suspension from the exercise program will be the most common reason for missing outcomes data in both arms. We have designed the testing windows to minimize missing data. At months 3 and 6, testing will be allowed within a window of  $\pm 2$  weeks. At months 9 and 12, testing will be allowed within a window of  $\pm 1$  month, making the total participation time up to 13 months from the baseline in-clinic study visit (C00). Despite our efforts at follow-up, some missing data are expected with multiple testing visits. We will collect the reasons for missing data such as death, COPD exacerbation, medical reasons, or non-medical reasons. We will compare the rate of losses to follow-up at 3, 6, 9, and 12 months among the two arms using the chi-square test of association. We will assess whether any baseline characteristics such as age, FEV1 % predicted, or 6MWT distance, are associated with losses to follow-up using chi-square tests for categorical baseline data and analysis of variance for continuous baseline data. If baseline variables and treatment group are found to be associated with loss to follow-up, then the analysis models will be modified to include the differing baseline variables as covariates to provide unbiased estimates of intervention effects. For subjects who discontinue the study early due to worsening of COPD or due to death, missing outcome data will be imputed using the least favorable data observed prior to discontinuation. Missing data for subjects who miss a visit not related to worsening of COPD will be imputed using last observed data. We will also perform sensitivity analyses using the complete case method, excluding those with no observed outcome at 6 months.

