### **Statistics (power analysis)**

Prior to analyzing the outcomes, we will summarize and compare baseline demographic and clinical variables by treatment group. Any unbalanced characteristics occurring despite randomization will be assessed as potential confounders in multivariate analyses. Analyses will be performed with the SAS statistical software package (9.3, SAS Institute; Cary, NC).

**Primary Aim:** To determine the efficacy of the WEB intervention to increase 6MWT distance.

We focus on 6MWT distance at 6 months since we predict that the greatest difference in 6MWT distance between study arms will occur at month 6, at the end of the interventional phase. We have revised our statistical analysis plan to use 2-way factor analysis or analysis of variance (ANOVA). This approach will assess the effect of intervention versus control on 6MWT distance, using absolute measures of 6MWT distance at baseline and 6 months. Two-way ANOVA will allow us to assess the effect of treatment (intervention versus control), and additionally allow us to assess the interaction between treatment and time (treatment-time) on 6MWT distance. We will use a mixed model (PROC MIXED in SAS) to perform the 2-way ANOVA given its flexibility of modeling the variances and covariances, its robustness in accounting for correlated data (repeated measures data), and its flexibility in handling missing data. Models will have 6MWT distance as the dependent variable, and treatment, time, and treatment-time as independent variables. In this approach, models will also include study site and any unbalanced baseline characteristics as covariates. Primary analyses to determine the effect of WEB on 6MWT distance will use the intention-to-treat approach to include as many randomized subjects as possible in the analyses. Subjects will be considered to be in his/her randomly assigned arm no matter how much he/she participated in it. As a sensitivity analysis, however, we will examine 6MWT distance on a per-protocol basis, where noncompliant subjects ( $\geq 30\%$  of days with no exercise performed on logs) in each treatment arm will be excluded from the analysis.

**Anticipated Results:** We anticipate that subjects in the intervention group will have significantly higher 6MWT distance than subjects in the control group at 6 months.

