**Power Calculation:** This study is powered on our pre-specified primary outcome of 6MWT distance. Our main comparison is 6MWT distance at 6 months between the WEB intervention and control arms. Our power analysis is based on a widely accepted minimum clinically meaningful change in 6MWT distance of 54 meters and the published standard deviation for 6MWT distance of 80-120 meters (90). Our data in a similar Veteran population showed a standard deviation of 102 meters for 6MWT distance. We use a standard deviation of 100 meters in our power calculation. Using the sample size formula for the comparison of the means of 2 independent samples, we calculate that 55 evaluable subjects in each arm at 6 months will allow

[figure not shown]

detection of a difference of at least 54 meters between the WEB and usual care arms with a power of 80% and  $\alpha=0.05$ . We anticipate a maximal drop-out of 40% at 6 months. In order to have 111 evaluable subjects at 6 months, we plan to enroll a total of 185 subjects.

**Secondary Aims:** To estimate the effect of the WEB intervention on (a) HRQL, as measured by the St. George's Respiratory Questionnaire (SGRQ), (b) dyspnea, (c) CRP and IL-6, (d) risk of AEs and COPD-related hospitalizations, (e) engagement in PA as measured by daily step count, (f) body composition and bone mineral density, and (g) pain.

Our statistical analysis plan for the secondary outcomes is similar to that for the primary outcome. We will use 2-way factor analysis or analysis of variance (ANOVA) to assess the effect of intervention versus control on SGRQ-TS, dyspnea score, CRP and IL-6, and daily step count. We will analyze absolute values of the secondary outcomes at baseline and 6 months. Two-way ANOVA will allow us to examine the effect of our intervention, and additionally allow us to assess the interaction between treatment and time (treatment-time) on the secondary outcomes. We will use a mixed model (PROC MIXED in SAS) to perform the 2-way ANOVA. Models will have SGRQ-TS, dyspnea score, CRP and IL-6, or daily step count as the dependent variable, and treatment, time, and treatment-time as independent variables. Models will also include study site and any unbalanced baseline characteristics as covariates.

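### Drop-out predictors enter the models only if two weak tests both flag loss, and neither test looks for loss patterns that differ by arm

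*Combined protocol and SAP*

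**What the plan says.** In the Combined protocol and SAP, the section Minimizing Attrition and Handling Missing Data sets up two kinds of test. For arm: "We will compare the rate of losses to follow-up at 3, 6, 9, and 12 months among the two arms", by chi-square. For baseline characteristics, with age, FEV1 % predicted and 6MWT distance as examples, loss is examined "using chi-square tests for categorical baseline data and analysis of variance for continuous baseline data". The consequence follows: "If baseline variables and treatment group are found to be associated with loss to follow-up, then the analysis models will be modified". The modification is spelled out as a step "to include the differing baseline variables as covariates to provide unbiased estimates of intervention effects".

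Read literally, both associations are needed. No significance level is given, nor a fixed list of covariates, nor a test of whether a baseline variable predicts loss differently in the two arms.

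Three other provisions apply whatever these tests show:
- The same section imputes missing outcomes by single values (least favorable or last observed, depending on the reason) and adds a complete-case sensitivity analysis.
- Statistics (power analysis) fits a mixed model to 6MWT at baseline and 6 months, so baseline 6MWT is always present as a repeated outcome.
- On covariates, that section says: "In this approach, models will also include study site and any unbalanced baseline characteristics as covariates".

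The planning assumption there is "We anticipate a maximal drop-out of 40% at 6 months", and Table 2 expects "Most common cause of missing data (health reasons) will be same for both arms".

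**The concern.** A covariate rule that depends on a test is only as good as the test. Here two tests must both succeed, in a trial sized for a 54 m difference in 6MWT and not for detecting attrition patterns.

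The tests also ask a different question from the one that matters. The comparison is biased when the people lost differ between arms. That can happen with identical loss rates and with no overall association between the baseline variable and loss. If one arm tends to lose its sicker members and the other its fitter ones, both marginal tests can be null while the completers are not comparable.

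Arm-specific loss is plausible. Only WEB subjects have a year of pedometer wear, uploads, website use and weekly goal calls (Pedometer and Internet-mediated walking program), while controls return the pedometer after baseline (Randomization). Table 2's statement about a common cause is an expectation, not a finding.

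The covariates chosen for baseline imbalance do not close the gap. They come from comparing the treatment groups at baseline, not the completers. At stake is an effect estimate with up to 74 of 185 month-6 values missing (0.40 × 185 = 74), and a covariate set that depends on post-randomization data.

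**Working it through.** **1. The plan's own figures.** Difference 54 m, SD 100 m, 80% power, α = 0.05 (two-sided assumed). n per arm = 2(1.960 + 0.842)² × 100² / 54² = 53.8, so 54; the t-test gives 80.1% power at 55. With 40% loss, 111 / 0.60 = 185. Both stated figures reproduce.

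**2. Arm test.** Inputs: 92.5 per arm, 40% average loss, 5% two-sided (assumed). Power = Φ[(Δ − 1.96·SE₀)/SE₁], with SE₀ = √(2 × 0.40 × 0.60 / 92.5) = 0.0720 and SE₁ = √[(p₁q₁ + p₂q₂) / 92.5].
- 35% vs 45%: SE₁ = 0.0717; Φ[(0.10 − 0.1412)/0.0717] = 28%. Missed about 72% of the time; direct simulation with 92 vs 93 gives 71%.
- 32.5% vs 47.5%: 55%. Missed about 45% (44% by simulation).
- 30% vs 50%: 80%. Missed about 20%.

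**3. Baseline test.** 111 retained vs 74 lost; noncentrality = d / √(1/111 + 1/74) = d / 0.150, on 183 df.
- d = 0.3: noncentrality 2.00, power 51%, missed 49%.
- d = 0.4: power about 75%, missed about 25%.
- 80% power needs d = 2.80 × 0.150 = 0.42.

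**4. How often the joint rule fires.** Simulation with no treatment effect and N = 185. Loss is logistic in a baseline predictor, with assumed strengths per SD.

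| Selection pattern (log-odds per SD) | Loss by arm | Both tests fire |
|---|---|---|
| Opposite by arm (∓0.5 to 0.8) | 40% / 40% | under 1% |
| WEB only (−0.8) | 40% / 40% | 3–4% |
| WEB only (−0.8) | 45% / 35% | about 20–22% |
| WEB only (−0.8) | 47.5% / 32.5% | about 40% |

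If either test were enough, the first row would rise only to about 9%.

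**5. Size of the bias in observed data.** Further assumptions: residual SD of 6MWT change 60 m; change varies by 15 to 30 m per SD of the predictor. The bias is roughly that slope times the difference between arms in the completers' mean predictor.
- Opposite selection: about 6 to 17 m, type I error about 7% to 27%. Check on the top end: SD of change = √(60² + 30²) = 67 m; SE = 67 × √(2/55.5) = 12.7 m; 17/12.7 = 1.34; P(Z > 1.96 − 1.34) ≈ 27%.
- WEB-only selection: about 4 to 10 m, type I error about 6% to 13%.
- Always adjusting for the predictor: under 0.4 m, type I error about 4% to 6%.
- Same selection in both arms: about 0 to 2 m.

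A separate simulation without baseline 6MWT, with the predictor correlated 0.3 to 0.5 with the month-6 value and weaker selection (0.5 per SD), put the gated estimate off by about 12 to 19 m (opposite selection) and 6 to 9 m (one arm only, about a 10-point gap). It ignores a variable that the primary model contains, so the 4 to 17 m range is the better guide.

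**6. The same set-up with single imputation.** Simplified to carrying baseline forward for every drop-out, with opposite selection at 40%/40% and slope 30. The 40% who are lost contribute zero change, so 0.60 × 17.0 = 10.2 m of bias should remain. Simulation gives 10.2 m unadjusted and 10.1 m adjusted (a second run gives 9.9 and 9.8 m), with type I error of 27% and 29%. Adjustment does nothing here: all randomized subjects are analysed, and the predictor is balanced across them by randomization.

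**The case against.** The strongest reply is that the bias figures belong to an observed-data analysis, whereas the attrition section imputes missing outcomes regardless of the tests and uses complete cases only as a sensitivity analysis. This stands in part. Step 6 shows that covariates leave the bias of the imputed analysis where it was, so a fix that changed only the conditional sentence would give false comfort. The gate offers no protection there either. Statistics (power analysis) also justifies the mixed model partly by its handling of missing data, so the observed-data analysis is one that the plan itself supports.

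A reader might infer that the plan treats a non-significant test as proof of no attrition bias. It says no such thing. Leaving the model unmodified is only the working effect of the gate, and reasons for missingness are still collected.

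A reader might also infer that no predictor of loss enters without a test. That is too strong: baseline 6MWT, one of the three named examples, is always in the primary model, with site and any characteristics unbalanced at baseline.

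Finally, the larger biases need selection that differs by arm, which the documents do not predict; they expect health reasons to dominate in both arms. If that holds and selection is the same, the gate does little harm. But the trial cannot count on it, and these tests would not reveal the contrary.

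**Conclusion.** The concern holds in limited form. The safeguard against attrition bias is conditional on two tests that often miss moderate associations and do not look for the pattern that causes bias. In the arm-differential scenarios examined, it stayed off in roughly 60% to more than 99% of trials.

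The cost in observed-data analyses is about 4 to 17 m, or 7% to 31% of the 54 m target (4/54 and 17/54), and about 0 to 2 m if selection is the same in both arms. The test-power figures rest on the plan's numbers and an assumed 5% two-sided level. The bias figures rest on assumed slopes, selection strengths and residual SD, so they are a range of what could happen and not a forecast.

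For the primary outcome the gap concerns predictors other than baseline 6MWT. The documents do not support the further inference that covariate adjustment would clear attrition bias from every planned analysis: with baseline carried forward, about 60% of it remains.

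**What to change.** In Minimizing Attrition and Handling Missing Data, replace the conditional sentence with a fixed rule:
- The observed-data mixed model of Statistics (power analysis) and the complete-case analysis always include age and FEV1 % predicted, and the secondary-outcome models also include baseline 6MWT, whatever the loss tests show.
- Enter age and FEV1 % predicted with a covariate-by-time term so that they act on the month-6 value. A main effect alone shifts baseline and month 6 equally and leaves the treatment-by-time contrast largely untouched.
- Keep the loss comparisons as description: loss by arm with 95% confidence intervals, and characteristics of lost and retained subjects within each arm.
- State that this adjustment does not remove attrition bias from an analysis using last-value or least-favorable imputation. For the primary outcome, therefore, report the adjusted observed-data mixed model, or a multiple-imputation model containing the same predictors by arm.

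The cost is one paragraph of analysis-plan text, two or three model degrees of freedom, and a simple rule for missing baseline values. No new data are needed.

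### The plan does not say whether single imputation or the mixed model without imputation governs the primary 6MWT analysis; the choice can move the estimate materially near 40% loss

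*Combined protocol and SAP*

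**What the plan says.** Under Minimizing Attrition and Handling Missing Data there are two filling rules. For early discontinuation through COPD worsening or death, "missing outcome data will be imputed using the least favorable data observed prior to discontinuation". For other missed visits, "Missing data for subjects who miss a visit not related to worsening of COPD will be imputed using last observed data". The section then adds: "We will also perform sensitivity analyses using the complete case method, excluding those with no observed outcome at 6 months". Table 2 condenses the rules to "Impute with least favorable value or carry forward previous values".

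The Primary Aim text under Statistics (power analysis) describes a revised plan. It fits PROC MIXED to 6MWT distance at baseline and 6 months with treatment, time and their interaction, under intention to treat. One of its stated reasons for the mixed model is how it deals with incomplete data. It does not mention imputation. Additional Analyses uses the same procedure on all visits, again without mentioning imputation.

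Neither section refers to the other. The Primary Aim text also says "we predict that the greatest difference in 6MWT distance between study arms will occur at month 6".

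**The concern.** The two sections suggest different primary analyses. If missing values are filled first, the mixed model receives complete data and the missing-data reason for choosing it has no role. If they are not filled, the imputation rules have no stated place in the primary result. The data used also differ: the primary model takes only baseline and month 6, so a later drop-out's month-3 value can enter only through imputation.

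At stake are the size of the primary estimate and the honesty of its interval. A carried-forward value is treated as a measured month-6 value, although the plan expects the arms to differ most at month 6. Without a fixed rule, the primary result is also not uniquely defined before the data are seen.

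**Working it through.** **Inputs from the documents.** Difference 54 m, SD 100 m, 80% power, alpha 0.05, 55 evaluable per arm, 111 evaluable in total, 185 enrolled, drop-out at most 40% (Power Calculation); loss of 0 to 4% at 12 months in the investigators' other COPD studies (Minimizing Attrition); 6MWT at baseline, 3 and 6 months (Table 5).

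**Assumptions not in the documents.** Two-sided test; 92 or 93 per arm; equal correlation r between visits; true effect 54 m at month 6 and 27 m at month 3; half of drop-outs lost before month 3; loss equal between arms and unrelated to outcome unless stated.

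**1. The plan's own figure.** n per arm = 2 × (1.96 + 0.84)² × 100² / 54² = 53.8, so 54; the t-test version gives 54.8, so 55. Enrollment: 111 / 0.60 = 185. Both reproduce. At 40% loss, 0.40 × 185 = 74 participants depend on the missing-data rule.

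**2. What the last-value rule assigns.** Someone lost before month 3 has only a baseline value, so the assigned change is exactly zero; the least-favorable rule gives the same, even after death. A later drop-out is assigned the month-3 value. With loss d, expected estimate = (1 − d) × 54 + (d/2) × 27. Coverage of 54 m is from simulation (2,500 replicates per setting).

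| Loss | Expected estimate | 95% CI coverage at r = 0.5 / 0.8 / 0.9 |
|---|---|---|
| 4% | 0.96×54 + 0.02×27 = 52.4 m | 95 / 95 / 94% |
| 10% | 0.90×54 + 0.05×27 = 50.0 m | 93 / 93 / 89% |
| 20% | 0.80×54 + 0.10×27 = 45.9 m | 91 / 85 / 78% |
| 40% | 0.60×54 + 0.20×27 = 37.8 m | 77 / 53 / 29% |

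The two-visit mixed model on observed values gives 53 to 54 m with 94 to 96% coverage throughout.

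**3. Why coverage falls (40% loss, r = 0.8).** The variance of a change is 2 × 0.2 × 100² = 4,000 (SD 63.2 m). Early drop-outs contribute none. Control variance: 0.8 × 4,000 = 3,200. WEB variance: 3,200 + (0.6×54² + 0.2×27² − 37.8²) = 3,667. SE = √((3,667 + 3,200)/92.5) = 8.6 m. The shift of 54 − 37.8 = 16.2 m is 1.9 SEs. The mixed model's simulated SE is 11.8 m (observed changes alone: √(2 × 4,000/55.5) = 12.0 m).

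**4. Least-favorable rule for half of drop-outs (40%, r = 0.8).** For late drop-outs the expected value of min(0, change) is −25.2 m in control and −14.0 m in WEB, a difference of 11.2 m. Estimate: 0.6×54 + 0.2×(0.5×27 + 0.5×11.2) = 36.2 m.

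**5. Range and direction.** At 40% equal loss:
- all lost before month 3: 0.6×54 = 32.4 m;
- full effect by month 3, half lost earlier: 0.6×54 + 0.2×54 = 43.2 m;
- full effect by month 3, all drop-outs seen then: 54 m;
- month-3 effect 70 m, all seen then: 0.6×54 + 0.4×70 = 60.4 m, away from zero.

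Unequal loss can also push the estimate up with a month-6 peak. Take 10% loss in WEB and 50% in control, the least-favorable rule for all, all seen at month 3, and 90% of the effect (48.6 m) present then. WEB: 0.9×54 + 0.1×(−8.0) = 47.8 m. Control: 0.5×(−25.2) = −12.6 m. Difference: 60.4 m.

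With no effect and a common decline, half of it by month 3, the last-value bias is 0.75 × decline × loss difference. For 30 m and 50% v 30% loss: 0.75×30×0.2 = 4.5 m, with simulated type I error of 7 to 8%.

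**6. Dependence on the target.** If lost WEB participants keep a fraction k of the benefit, the all-randomized effect at 40% loss is 0.6×54 + 0.4×54×k = 32.4 + 21.6k. The last-value result (37.8 m) is exact at k = 0.25. It is closer than the mixed model's 54 m whenever k is below (45.9 − 32.4)/21.6 = 0.63, where 45.9 is the midpoint of 37.8 and 54.

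**The case against.** **The attrition section settles it.** Its wording is directive, and naming complete case as the sensitivity analysis implies that imputation is the main approach. Imputing and then fitting PROC MIXED can be done, and the other reasons given for the mixed model (covariance modeling, correlated data) would survive. This is a fair inference. A reader might go further and infer that the Primary Aim text forbids imputation or specifies observed data only; it does neither. What stands is that the revised text cites missing data as a reason for its model and is silent on the earlier rules.

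**Retention may be good.** At the 0 to 4% loss seen in the investigators' other studies the distortion is about 2 m or less. That stands, but the trial was sized for up to 40%.

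**Carrying values forward is conservative, and the mixed model is not always better.** A reader might infer that imputation always shrinks the effect, or always costs power. Neither is supported. Step 5 shows estimates moving away from zero. At 40% equal loss simulated power is similar under last-value and mixed model (81% v 84% at r = 0.5; 99% v 99% at r = 0.8). The mixed model is assured unbiased only under missing at random, whereas the plan expects that "medical problems and temporary suspension from the exercise program will be the most common reason for missing outcomes data in both arms". In one simulated case of informative loss (50% WEB v 30% control, no effect, no common decline), type I error was 6% for last-value and 11 to 13% for the mixed model. Table 2's expectation, "Most common cause of missing data (health reasons) will be same for both arms", supports similar loss between arms but does not make it unrelated to outcome.

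**Safeguards exist.** Comparison of loss by arm, covariate adjustment, complete case and the all-visit model are all planned and would help expose a divergence. They do not say which result is primary. Adjustment offered "as covariates to provide unbiased estimates of intervention effects" cannot be relied on if loss depends on unobserved decline. Nothing suggests that the investigators intend to choose after seeing the data; the plan simply leaves that open.

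**Conclusion.** The gap is real: single imputation is the only explicit missing-data rule, the revised primary analysis does not mention it, and no text links the two. If imputation governs, a true 54 m would be reported as roughly 38 m at 40% loss, with 29 to 77% interval coverage depending on correlation, but as 50 to 52 m at 4 to 10% loss. These figures require similar loss unrelated to outcome, an effect still growing to month 6, the assumed timing of loss, and a target of the effect had drop-outs stayed. Under unequal or informative loss the direction is open, and if drop-outs lose most of the benefit the last-value result may be nearer the all-randomized effect. The harm is to the estimate and its interval under those conditions, not to power. Severity: should-fix.

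**What to change.** Before outcome data are seen, bring Table 2, Minimizing Attrition and Handling Missing Data, the Primary Aim text and Additional Analyses into agreement:

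- State that the primary 6MWT result is the month-6 treatment contrast from the likelihood-based PROC MIXED model on observed values, without single imputation. Including the month-3 value, already collected, is optional.
- Keep the last-value, least-favorable and complete-case analyses as sensitivity analyses.
- Add one delta-adjusted or reference-based sensitivity analysis, because health-related loss is expected and missing at random may fail.

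The cost is a few sentences and one extra analysis. The reported SE will be larger at r = 0.8: about 8.6 to 11.8 m at 40% loss and about 9.1 to 9.8 m at 10%. That increase reflects no longer counting filled-in values as measurements.
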